4.1 Duration of Study Participation

The duration of study participation will include the completion of surveys after a routine clinical visit (remotely or in-person) as well as one research (ultrasound) visit – total time in the study estimated to be approximately one month.

4.2 Total Number of Subjects and Sites

Patients may be recruited from Penn Medicine practices including PCAM, PMUC, Radnor, Valley Forge, and Cherry Hill. It is expected that approximately 40 subjects total will be consented in order to produce 20 total evaluable subjects.

4.3 Inclusion Criteria

- Age ≥18
- Meet ACR 2010 Criteria for RA
- Treatment with a disease-modifying anti-rheumatic drug (DMARD)
- Clinical Disease Activity Index (CDAI) > 10 (Composite score: Swollen Joint Count + Tender Joint Count + Patient Global Score + Physician Global Score)
- Swollen joint count ≤2

4.4 Exclusion Criteria

- Evidence of significant large joint activity with warmth and swelling (knee, hip, shoulder, elbow)

CONFIDENTIAL

- Joint MRI or musculoskeletal ultrasound in the past 3 months

4.5 Subject Recruitment

Patients scheduled for an upcoming rheumatology appointment at PCAM, PMUC, Radnor, Valley Forge, or Cherry Hill with a rheumatology provider who has opted-in to participate in the study will be pre-screened using EPIC to confirm that they meet criteria for RA, are receiving a DMARD, and are ≥ 18 years old. If providers find that a particular patient might meet the eligibility criteria, they can also refer their patient to the research team.

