5. C-reactive protein (CRP): Substance secreted by the liver. Routine blood test performed as part of standard clinical care to measure inflammation and assess disease activity in RA.
6. Musculoskeletal ultrasound (see below)

Chart review to obtain additional participant information:

- Demographics: Age, sex, race/ethnicity, BMI, smoking
- Medical History: RA disease duration, RF, CCP, current DMARDs, current glucocorticoid dose, current NSAID use, opioid use, number of previous biologics/JAKi
- Comorbidities: Presence of peripheral joint osteoarthritis, chronic back pain/back osteoarthritis, anxiety, depression, sleep apnea, fibromyalgia

Provider measures:

1. Pre-ultrasound assessment/treatment form:
 - Assessment of the patient's disease activity: providers will select whether they think the patient is in remission, low, moderate, or high disease activity (does not need to match the patient's CDAI score)
 - Confidence in the disease activity assessment (1-10) on a visual analog scale (VAS). A VAS tries to measure a characteristic or attitude that is believed to range across a continuum of values and cannot be easily directly measured.
 - Treatment recommendations: Providers will be asked whether their recommendation for treatment is as follows: no change, increase disease modifying anti-rheumatic drugs (DMARD) dose, or add/switch DMARD.
2. Post-ultrasound assessment/treatment form:
 - Same as the pre-ultrasound form but completed after ultrasound results are reviewed

Musculoskeletal ultrasound assessment

- Bilateral hands/wrists with gray-scale and power doppler (to be performed by the musculoskeletal ultrasound department or by an ultrasound certified rheumatologist within 3 weeks of visit 1. Synovitis in the metacarpophalangeal joint (MCPs), proximal interphalangeal joint (PIPs), and wrists will be graded as absent, mild, moderate, or severe according to the validated OMERACT scoring system. Images will be stored to allow a second reader to score images to assess inter-rater reliability.
 - OMERACT is the acronym for an international, informally organized network initiated in 1992 aimed at improving outcome measurement in rheumatology. Data driven recommendations are prepared and updated by expert working groups. Recommendations include core sets of measures for most of the major rheumatologic conditions
 - Patients in whom all measured joints have absent or mild synovitis will be considered to have low synovitis scores

CONFIDENTIAL

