3.4.2 Secondary Study Endpoints

The frequency of changes in physician treatment recommendations after ultrasound will be calculated. Fisher's exact tests will be used to compare the proportion of patients for whom treatment escalation (dose increase or DMARD add/switch) is recommended before versus after ultrasound. Differences in disease activity assessment before and after ultrasound will also be compared with Fisher's exact tests, and differences in the provider's confidence in disease activity assessment (5-point Likert scale) before and after ultrasound will be compared with the nonparametric Wilcoxon Signed Rank test.

4. Study Population and Duration of Participation

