6.1 Sample Size and Power Determination

This pilot and feasibility study will provide data to support power calculations for subsequent studies. Thus, the sample size was derived based on other considerations such as feasibility and cost.

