6.3.2 Analysis of Primary Outcome of Interest

Aim 1 Analysis: The proportion of included patients with low synovitis scores will be calculated. To assess patient characteristics associated with having low synovitis scores to inform inclusion criteria for a future interventional study, Fisher's exact tests will be used to compare the proportion of low synovitis scores in patients in certain prespecified subgroups:

- patients with long-standing versus earlier RA (>5 years vs ≤ 5 years)
- biologic vs. non-biologic treated patients, high versus low CRP (>1 mg/dL vs. ≤ 1 mg/dL)
- patients with vs. without evidence of central pain sensitization (PSD ≥ 12 vs < 12)
- seropositive vs. seronegative
- patients with depression vs. those without (based on PROMIS vs. PHQ-9)
- moderate vs high disease activity by DAS28 and moderate vs high disease activity by CDAI
- associations with age, comorbidities, CDAI, DAS28, will also be assessed.

Aim 2 Analysis: The frequency of changes in physician treatment recommendations after ultrasound will be calculated. Fisher's exact tests will be used to compare the proportion of patients for whom treatment escalation (dose increase or DMARD add/switch) is recommended before versus after ultrasound. Differences in disease activity assessment before and after ultrasound will also be compared with Fisher's exact tests, and differences in the provider's confidence in disease activity assessment (5-point Likert scale) before and after ultrasound will be compared with the nonparametric Wilcoxon Signed Rank test.

7. Safety and Adverse Events

Adverse events related to study participation are expected to be uncommon. Serious adverse events assessed as possibly, probably, or definitely related to the study will be reported to the IRB according to IRB reporting requirements. Events will only be recorded and reported if they occur during the subject's participation in the study (up until the completion of the ultrasound visit).

CONFIDENTIAL

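### Aim 2 outcomes are provider judgements analysed as independent patients; if providers respond differently to ultrasound, the confidence test, and any simple interval for the change frequency, will be too precise

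*Combined protocol and SAP*

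**What the plan says.** Recruitment runs through providers. Section 4.5 takes patients with an appointment "with a rheumatology provider who has opted-in to participate in the study" and also lets providers refer their own patients. Section 4.2 lists five practices ("Patients may be recruited from Penn Medicine practices including PCAM, PMUC, Radnor, Valley Forge, and Cherry Hill"). No section gives the number of providers or a limit on patients per provider.

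The Aim 2 data are provider ratings. Section 3.3 has the provider choose an activity category, rate confidence in it and state a treatment recommendation ("Providers will be asked whether their recommendation for treatment is as follows"). The same form is completed again after the ultrasound results have been reviewed.

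The analysis in 3.4.2 and 6.3.2 is by patient:
- **Change frequency:** "The frequency of changes in physician treatment recommendations after ultrasound will be calculated". No interval is specified.
- **Escalation:** Fisher's exact test on "the proportion of patients for whom treatment escalation (dose increase or DMARD add/switch) is recommended before versus after ultrasound".
- **Activity rating:** "Differences in disease activity assessment before and after ultrasound will also be compared", again with Fisher's exact test.
- **Confidence:** Wilcoxon signed rank test, before versus after.

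Provider clustering is not mentioned. Section 6.3 rules out adjustment for confounding because the aim is to describe how common synovitis is. That reason belongs to Aim 1 and does not bear on correlated ratings in Aim 2.

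**The concern.** Two patients rated by the same provider share that provider's view of ultrasound. A provider who trusts it may revise most recommendations and gain confidence each time, while a sceptic may revise none. The signed rank test pairs the two ratings of one patient, but it takes the differences as independent across patients. If providers vary in how they change, those differences are correlated and the test rejects too often.

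The same holds for the change frequency if someone attaches a binomial interval to it. With 20 evaluable patients, a provider contributing five would supply 5/20 = 25% of the Aim 2 data, and the pooled frequency alone would not show it.

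Section 6.1 says the pilot is meant to support power calculations for later studies. A later trial that took the Aim 2 result at its face-value sample size would start from too much apparent information, and would have no description of how much providers differ.

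**Working it through.** **The plan's own figure.** Section 4.2 expects that "approximately 40 subjects total will be consented in order to produce 20 total evaluable subjects", and 6.1 says "the sample size was derived based on other considerations such as feasibility and cost". No alpha, power, effect size or design effect is given, so there is no derivation to reproduce. Both n = 20 and n = 40 are carried below.

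**Assumptions (not in the documents).** Patients per provider m, equal across providers; intraclass correlation (ICC) of the change indicator; change frequency p = 0.30; two-sided alpha 0.05.

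**Step 1: precision of the change frequency.** Design effect DE = 1 + (m − 1) × ICC; effective n = n/DE; 95% half-width = 1.96 × √(p(1 − p) × DE/n).

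If patients are independent, n = 20 gives 1.96 × √(0.21/20) = 20.1 points and n = 40 gives 1.96 × √(0.21/40) = 14.2 points.

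| m | ICC | DE | Width factor √DE | Effective n of 20 / of 40 | Half-width, n = 20 / n = 40 (points) |
|---|---|---|---|---|---|
| 1 | any | 1.0 | 1.00 | 20 / 40 | 20.1 / 14.2 |
| any | 0 | 1.0 | 1.00 | 20 / 40 | 20.1 / 14.2 |
| 3 | 0.1 | 1.2 | 1.10 | 16.7 / 33.3 | 22.0 / 15.6 |
| 4 | 0.1 | 1.3 | 1.14 | 15.4 / 30.8 | 22.9 / 16.2 |
| 4 | 0.3 | 1.9 | 1.38 | 10.5 / 21.1 | 27.7 / 19.6 |
| 5 | 0.3 | 2.2 | 1.48 | 9.1 / 18.2 | 29.8 / 21.1 |

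**Step 2: which correlation matters for the before/after tests.** Let D be a patient's after-minus-before difference, σ² the variance of one rating and ρ the correlation between a patient's two ratings. Then Var(mean D) = 2σ²(1 − ρ) × [1 + (m − 1) × ICC of D]/n. A provider tendency that affects both ratings equally drops out of D, so only variation between providers in the *change* does harm. A paired test that ignores provider is wrong by the bracketed factor. An unpaired test assumes 2σ²/n, so its variance is wrong by (1 − ρ) times that factor. It becomes too liberal only when clustering of the change outweighs the pairing.

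**Step 3: simulated type I error at nominal 0.05.** Latent normal model, escalation rate 50%, variance shared by a patient's two ratings 0.5, 4,000 runs per scenario (Monte Carlo standard error at 0.05: √(0.05 × 0.95/4000) = 0.003). Ranges cover n = 20 and n = 40.

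| ICC of change | m | Fisher (unpaired, as planned) | Exact McNemar | Wilcoxon signed rank |
|---|---|---|---|---|
| 0 | 1 to 10 | 0.004–0.010 | 0.013–0.026 | 0.044–0.054 |
| 0.1–0.2 | 4–5 | 0.008–0.031 | 0.022–0.059 | 0.078–0.145 |
| 0.1–0.2 | 10 | 0.025–0.055 | 0.047–0.095 | 0.146–0.249 |
| 0.4 | 4–5 | 0.035–0.050 | 0.059–0.10 | 0.18–0.22 |
| 0.4 | 10 | about 0.12 | 0.16–0.18 | 0.37–0.38 |

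With one patient per provider, the Wilcoxon test stays at 0.044 to 0.054 even when the ICC of change is 0.1 to 0.4. The ICC here refers to the latent change, so it is not interchangeable with the ICC of the yes/no indicator in Step 1.

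**The case against.** Three stronger readings are tempting, and the documents support none of them.

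- **That every provider rates several patients.** A reader might infer this from provider-based recruitment. Section 4.5 says only that the provider has opted in. With five practices, some providers may contribute a single patient. Clustering is plausible but not established.
- **That all the before/after p-values are too small.** The two Fisher comparisons treat a patient's two ratings as separate samples. Under the pairing assumed above, this makes them conservative: at most 0.031 for m up to 5 and an ICC of change up to 0.2. They clearly exceed 0.05 only with strong clustering and large clusters. For these tests the lost pairing is the larger fault, and it works in the opposite direction.
- **That the planned interval for the change frequency is too narrow.** No interval is planned. The frequency itself remains valid as a patient-weighted average.

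The trial team can add that this is a secondary aim of a pilot that 6.2 calls descriptive, with hypothesis testing left to a larger proposal, and that 6.1 does not name the Aim 2 frequency as an input to later power calculations. That is fair and keeps the point minor. It does not remove it, because the plan does specify a signed rank test, and any later user of the frequency will need some measure of its precision.

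It is also fair that cluster methods are weak here. At m = 3 to 5, 20 patients mean about 4 to 7 providers (20/5 to 20/3) and 40 mean about 8 to 13. That argues for a modest sensitivity analysis rather than a clustered model as the main method.

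**Conclusion.** The point holds in a conditional form. Aim 2 rests on provider judgements, and the plan has nothing for correlation within provider. If providers differ in how they respond to ultrasound, the signed rank test on confidence is anti-conservative: a type I error of 0.078 to 0.145 against 0.05 at 4 to 5 patients per provider and an ICC of change of 0.1 to 0.2. Under the same condition, a simple binomial interval for the change frequency, or the raw n used in planning, would overstate the information by a factor of 1.2 to 2.2 at 3 to 5 patients per provider and ICC 0.1 to 0.3. That leaves an effective 9 to 17 of 20 patients, or 18 to 33 of 40.

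All of these sizes rest on assumed cluster sizes and correlations. The effect is nil with one patient per provider or zero correlation. The Fisher tests are not generally anti-conservative, and clustering becomes the relevant issue for them once they are replaced by paired tests. For a descriptive pilot this is a worthwhile improvement, not a serious flaw.

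**What to change.** In 3.4.2 and 6.3.2:

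1. Keep the provider ID with both the pre- and post-ultrasound forms, and report the number of providers and the patients per provider.
2. Analyse escalation and activity ratings before and after ultrasound as paired data, for example with an exact McNemar test for escalation and a paired ordinal method for the four activity categories.
3. Beside those unclustered paired results, give two sensitivity analyses for the change frequency and the confidence difference: a leave-one-provider-out check, and a provider-clustered interval with a small-sample correction.
4. Report any within-provider correlation as exploratory only. A handful of providers cannot supply a reliable planning value.

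The cost is some SAP wording and a few lines of code. No extra patients or visits are needed, and the provider link should already exist because results are emailed to each provider (5.2.2). The downside is wider intervals, and the clustered results are approximate when providers are few.

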4.6 Vulnerable Populations

Children, pregnant women, fetuses, neonates, or prisoners are not included in this research study.

5. Study Procedures

5.1 Pre-screening/Screening

Patients with scheduled visits in the rheumatology clinic will be pre-screened for age, RA diagnosis, and DMARD treatment. If patients who are being pre-screened have already completed the RAPID3 survey, the survey score will be assessed for eligibility.

Patients will be contacted through the My Penn Medicine patient portal to inform them about the study and to remind them to complete their RAPID3 survey (sent to all patients in the practice as part of routine care), with the option to opt-out of further pre-screening assessments. Patients without My Penn Medicine or who do not complete the RAPID3 survey will be contacted by phone to inform them about the study and to administer the RAPID3 survey if patients are interested in the study. Patients may still be recruited on the day of their clinic visit, even if a RAPID3 has not been measured or is low, if the patient meets inclusion criteria on the day of the clinic visit.

RAPID3 eligibility criteria:

If RAPID3 ≤ 6 :

- Patients will be informed through MPM and/or phone that they are not likely eligible for the study at this time but might be at a future visit. Providers can still refer these patients to the study and they can be included if they meet inclusion criteria on the day of their office visit.

If RAPID3 > 6 :

- Patients will be informed through MPM and/or phone that they may be eligible for the study depending on their routine exam in clinic.
- Providers will be notified of potentially eligible patients

Providers will perform routine standard of care assessment of disease activity using the CDAI (see 3.3 Study Measures) at the patient's clinic visit. If the score meets the study eligibility criteria, the patient will be approached either at the clinic visit or by phone and asked if they are interested in the study. If they are, the consent process will be conducted.

5.2 Post-screening Procedures

5.2.1 Visit 1

1. Informed Consent Process / HIPAA Authorization: All subjects for this study will be provided a consent form either in person or electronically describing the study and providing sufficient information for subjects to make an informed decision about their willingness to participate. See

CONFIDENTIAL

Attachment [consent form number] for a copy of the Informed Consent Form. This consent form will be submitted with the protocol for review and approval by the IRB for the study. The formal consent of a subject, using the IRB-approved consent form, must be obtained before that subject undergoes any study procedure. The subject, or legally acceptable surrogate, must sign the consent form in person or electronically, as well as the investigator-designated research professional obtaining the consent. Subjects will be consented by the Clinical Research Coordinator, PI, or Co-Investigator in a private room or by phone followed by electronic signature. Potential subjects will review the consent form in detail with the person designated to consent and have the ability to take the consent home for further review.

2. Patients will complete patient surveys in clinic or will be sent a REDCap link to complete surveys remotely (see 3.3 Study Measures)
3. Physicians will complete the pre-ultrasound assessment (see 3.3 Study measures) in person or will be sent a REDCap link to complete the survey remotely

5.2.2 Visit 2 (Ultrasound assessment)

1. Ultrasound scheduling:
 - After enrollment, the CRC will schedule musculoskeletal ultrasound with either a rheumatologist certified in MSK ultrasound or the Penn Division of Musculoskeletal Radiology (MSK Radiology).
2. During ultrasound visit:
 - If participants did not complete REDCap surveys during or after the clinic visit, then surveys can be done in person at the time of the ultrasound visit.
 - Ultrasound will be performed by trained staff.
3. After the ultrasound:
 - Synovitis will be graded according to the validated OMERACT scoring system.
 - All study visits are complete. Any study related patient questions can be answered by CRC.
 - Results of the ultrasound will be emailed to providers via encrypted email along with an interpretation based on OMERACT scoring and post-ultrasound assessment/treatment form (see 3.3 Study Measures)

5.3 Unscheduled Visits

Given the nature of the study unscheduled visits are not expected.

5.4 Subject Withdrawal

Subjects may withdraw from the study at any time without impact to their care. They may also be discontinued from the study at the discretion of the Investigator for lack of adherence to study procedures or ultrasound visit schedules or AEs. Subjects who withdraw early will not have further follow up or data collection. All data collected up until point of withdrawal will be used for analysis.

5.5 Safety Evaluation

All efforts to uphold patient safety will be obtained. Data and privacy protection will be ensured by administering surveys through Penn REDCap. Verbal and written consent will be obtained from potentially eligible or eligible participants before commencement of any study procedures. Staff performing the study ultrasound will have been properly trained. Although the potential for a confidentiality breach does exist, the research team will follow all standard procedures for training, consent, storage, and reporting to minimize potential exposure of patient information.

6. Statistical Plan

CONFIDENTIAL

The number of patients with evidence of synovitis on ultrasound will be tabulated and compared across key measures such as CDAI, depression scores, polysymptomatic distress questionnaire, and PROMIS pain. The analysis will also summarize and tabulate the number of patients for which the ultrasound information changed the decision-making of the clinical provider.

6.1 Sample Size and Power Determination

This pilot and feasibility study will provide data to support power calculations for subsequent studies. Thus, the sample size was derived based on other considerations such as feasibility and cost.

6.2 Statistical Methods

The statistical analysis will be performed by the study investigators using Stata statistical software (version 15). The goal of the analysis is to provide descriptive evidence to support a larger proposal where hypothesis testing and testing of interventions can be performed.

6.3 Control of Bias and Confounding

As the overall goal of the proposed study is to describe the prevalence of synovitis in this patient population, there will be no adjustment for confounding performed.

6.3.1 Baseline Data

Baseline and demographic characteristics will be summarized by standard descriptive statistics (including mean and standard deviation for continuous variables such as age and standard percentages for categorical variables such as gender).

6.3.2 Analysis of Primary Outcome of Interest

Aim 1 Analysis: The proportion of included patients with low synovitis scores will be calculated. To assess patient characteristics associated with having low synovitis scores to inform inclusion criteria for a future interventional study, Fisher's exact tests will be used to compare the proportion of low synovitis scores in patients in certain prespecified subgroups:

- patients with long-standing versus earlier RA (>5 years vs ≤ 5 years)
- biologic vs. non-biologic treated patients, high versus low CRP (>1 mg/dL vs. ≤ 1 mg/dL)
- patients with vs. without evidence of central pain sensitization (PSD ≥ 12 vs < 12)
- seropositive vs. seronegative
- patients with depression vs. those without (based on PROMIS vs. PHQ-9)
- moderate vs high disease activity by DAS28 and moderate vs high disease activity by CDAI
- associations with age, comorbidities, CDAI, DAS28, will also be assessed.

Aim 2 Analysis: The frequency of changes in physician treatment recommendations after ultrasound will be calculated. Fisher's exact tests will be used to compare the proportion of patients for whom treatment escalation (dose increase or DMARD add/switch) is recommended before versus after ultrasound. Differences in disease activity assessment before and after ultrasound will also be compared with Fisher's exact tests, and differences in the provider's confidence in disease activity assessment (5-point Likert scale) before and after ultrasound will be compared with the nonparametric Wilcoxon Signed Rank test.

7. Safety and Adverse Events

Adverse events related to study participation are expected to be uncommon. Serious adverse events assessed as possibly, probably, or definitely related to the study will be reported to the IRB according to IRB reporting requirements. Events will only be recorded and reported if they occur during the subject's participation in the study (up until the completion of the ultrasound visit).

CONFIDENTIAL

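### Every named Aim 1 association test uses a yes/no label fixed by the worst joint; the joint grades already collected should also get a supportive analysis.

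*Combined protocol and SAP*

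**What the plan says.** Section 3.3 (Musculoskeletal ultrasound assessment) covers the MCPs, PIPs and wrists of both hands, and synovitis "will be graded as absent, mild, moderate, or severe according to the validated OMERACT scoring system". It then reduces each patient to one label: "Patients in whom all measured joints have absent or mild synovitis will be considered to have low synovitis scores". A single moderate joint therefore makes a patient not low.

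The primary objective (2.1) is the frequency of that label. For the associations, sections 3.4.1 and 6.3.2 state "Fisher's exact tests will be used to compare the proportion of low synovitis scores in patients in certain prespecified subgroups". The final bullet of that list adds that "associations with age, comorbidities, CDAI, DAS28, will also be assessed" and names no method. The opening of section 6 adds a further patient count: "The number of patients with evidence of synovitis on ultrasound will be tabulated and compared across key measures". Section 3.3 also stores images so that a second reader can assess agreement. No section plans an association with a total score, a number of active joints or a maximum grade.

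On size, section 4.2 says "It is expected that approximately 40 subjects total will be consented in order to produce 20 total evaluable subjects", while the introduction and the Study Summary give 40. Section 6.1 explains that "the sample size was derived based on other considerations such as feasibility and cost".

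**The concern.** The Aim 1 associations are meant to guide who is enrolled in a later interventional trial. Each scan yields about 20 ordered grades, yet the named tests see one bit per patient. In a sample of 20 to 40, that can leave a real predictor with little chance of showing, and a missed predictor may be dropped from the next design. The outcome is coarsened whatever the predictor, so truly binary factors such as serostatus and biologic use are affected as well as those that are cut.

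**Working it through.** **Inputs from the plan.** Four verbal grades per joint and the worst-joint rule (3.3); Fisher's exact test on the label (3.4.1, 6.3.2); 20 evaluable (4.2) or 40 patients (Study Summary, introduction). There is no power figure to reproduce.

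**Assumptions, because the plan is silent.**
- Two-sided alpha of 0.05.
- Grades scored 0-3.
- 22 joints: 10 MCP + 10 PIP, counting the thumb interphalangeal joints, + 2 wrists. It is 20 without the thumb interphalangeal joints.
- About 50% of patients low.
- Group differences d of 0.8 (moderate) and 1.2 (large) patient-level SD.
- Splits of 10/10, 20/20 and 30/10.

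**Model 1: one normal trait, cut at its median.** The proportions low are Φ(d/2) and Φ(−d/2): 0.66 vs 0.34 at d = 0.8, and 0.73 vs 0.27 at d = 1.2. Fisher power is enumerated exactly. The comparator is a t-test on the uncut trait, with noncentrality d·√(n1·n2/(n1+n2)); for 20/20 and d = 0.8 this is 0.8 × √10 = 2.53. Relative loss = 1 − Fisher/t.

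| Split | d | Fisher | t-test | Relative loss |
|---|---|---|---|---|
| 10/10 | 0.8 | 13% | 40% | 1 − 0.133/0.395 = 66% |
| 20/20 | 0.8 | 36% | 69% | 1 − 0.363/0.693 = 48% |
| 30/10 | 0.8 | 29% | 57% | 1 − 0.292/0.570 = 49% |
| 10/10 | 1.2 | 33% | 72% | 1 − 0.328/0.718 = 54% |
| 20/20 | 1.2 | 73% | 96% | 1 − 0.731/0.959 = 24% |
| 30/10 | 1.2 | 62% | 89% | 1 − 0.623/0.893 = 30% |

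**Model 2: 22 simulated joints.** A patient effect moves all joints together. The ranges cover within-patient correlations of 0.2 to 0.6. Fisher on the label is compared with Wilcoxon rank-sum on the sum of grades.

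| Split | d | Fisher | Rank-sum | Relative loss at the range ends |
|---|---|---|---|---|
| 10/10 | 0.8 | 7-12% | 28-35% | 1 − 7/28 = 75%; 1 − 12/35 = 66% |
| 10/10 | 1.2 | 14-27% | 56-65% | 1 − 14/56 = 75%; 1 − 27/65 = 58% |
| 20/20 | 0.8 | 18-29% | 55-62% | 1 − 18/55 = 67%; 1 − 29/62 = 53% |
| 20/20 | 1.2 | 40-64% | 87-94% | 1 − 40/87 = 54%; 1 − 64/94 = 32% |

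**How much is the cut and how much is the test.** Under the null, Fisher rejects only about 2.0-2.5% of the time at 20/20 and 1.2-1.3% at 10/10; the rank-sum test rejects about 3-5%. The cut alone has large-sample relative efficiency φ(z)²/[p(1−p)], where z = Φ⁻¹(p): 0.64 at 50% low and 0.58 at 30% or 70% low. A test with 80% power then falls to Φ(√0.64 × 2.80 − 1.96) = 61%, or Φ(√0.58 × 2.80 − 1.96) = 57%. That is a relative loss of 1 − 61/80 = 24% to 1 − 57/80 = 29%. The rest of the gap belongs to Fisher's test.

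**The opposite case.** Suppose groups differ only in having one or two moderate joints (70% vs 30% low), with mild grades unrelated to group. At 20/20, power is 59% for Fisher, about 7-10% for the sum of grades and 66% for the number of moderate or severe joints. At 10/10, Fisher has about 24%, the sum 5% and the count 37%. The sum fails here; the count does not.

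**The case against.** The strongest reply is that the yes/no state is the target. Section 2.1 asks how often it occurs, section 3.3 defines it, and 6.3.2 looks for characteristics that go with it. Sections 6.2 and 6.3 call the work descriptive, with hypothesis testing left to a later proposal. This stands as far as the primary proportion and the Fisher comparisons are concerned, and both should stay. It does not explain why grades already recorded should play no part in associations that are meant to shape the next trial.

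Four stronger readings are tempting but not supported.

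- *The label ranks patients the wrong way round.* Twenty-two mild joints sum to 22 and count as low; one moderate joint with the rest absent sums to 2 and counts as not low. That is a reversal only if total burden is the target, and the plan does not make it so. In simulation it affected 0-9% of low/not-low pairs.
- *At least half the power is always lost.* This holds at 20 evaluable patients when the effect is spread across joints, but not for large effects at 40.
- *Every association is affected and the grades are thrown away.* The last Aim 1 bullet names no test. The grades are recorded and images kept for a second reader; what is missing is an association analysis that uses them.
- *A total score is simply better.* With focal disease it can be far worse, and because entry requires a swollen joint count of 2 or less (4.3), focal disease cannot be dismissed.

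**Conclusion.** The point holds as a limited, inexpensive improvement to the association analyses; it does not undermine the primary endpoint. When the effect is spread across joints, more than half the power is lost at 20 evaluable patients in every scenario examined. At 40, about half or somewhat more is lost for moderate effects. For large effects at 40 the loss is about a third to a half in the joint-level model, and as low as 24% in the single-trait model. These figures rest on assumed effect sizes, alpha, proportion low, joint count and subgroup splits, none of which the plan gives. Part of each loss comes from Fisher's conservatism and would remain with any binary outcome tested that way. Which size of loss applies also depends on whether 20 or 40 patients will be analysed, and the documents differ on this.

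**What to change.** Keep the low/not-low proportion as primary and keep the Fisher comparisons. In 3.4.1 and 6.3.2, add a prespecified analysis, labelled supportive, of each association on two graded outcomes:

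1. The number of joints graded moderate or severe. This is closest to the plan's own definition and still works if groups differ in only one or two active joints.
2. The sum of joint grades scored 0-3.

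Use Wilcoxon rank-sum for two-group factors and Spearman correlation for measured factors such as age, CDAI and DAS28, which would also supply the method missing from the last bullet. Report estimates with confidence intervals. List the joints scored and the 0-3 coding. State that the low/not-low result governs if the analyses disagree. Reconcile the 20 and 40 patient figures.

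The cost is a few lines of text and code, with no new data or visits. The downside is that two more outcomes per factor add comparisons in a small sample, so they should be presented as descriptive support and not as further tests to be won.
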